10.3 Safety Analysis

The safety will be assessed from the time of informed consent until the end of the

Follow-up Period. The Safety Population will be the primary population for the safety analysis. All safety endpoints will be summarized descriptively.

10.4 Sample Size

The assumption of this study is that the antihypertensive effect of finerenone is non-inferior to spironolactone. The sample size was based on data from our pilot study to assess the efficacy and safety of finerenone versus spironolactone in PA. According to pilot study, the standard deviation of 24-hour SBP were12.5mmHg in the finerenone group and 9.5mmHg in the spironolactone group respectively. Previous studies on antihypertensive RCT mostly set blood pressure in the range of 2-6 mmHg as the non-inferior limit $^{17-19}$, while the European Society of Hypertension pointed out that a difference of less than 5mmHg is clinically acceptable 20 . Therefore, the non-inferior limit is set as 4 mmHg. Using 80% power to measure the antihypertensive effect between the two groups, a unilateral significance level α =0.025, a total sample size of 244, an estimated dropout rate of about 20%, and a final sample size of 244/0.8=306, with a target of 153 patients per group.

11 Data Management and Record Keeping

A Data Safety Monitoring Board (DSMB) will meet periodically to monitor the study. The primary function of this committee is safety monitoring, and the committee will not discontinue the study for a finding of positive efficacy for any of the doses being considered. As part of these reviews, the DSMB will receive summaries of study conduct measures as well as safety and efficacy data. The DSMB may recommend discontinuing enrollment for a dose for safety or lack of efficacy.

The DSMB Chair is an expert in PA who is well-versed in GCP management. The Chair's responsibilities include facilitating discussions, integrating different perspectives, and reaching consensus among the responsible centers. The Chair is also committed to participating in DSMB activities throughout the trial period. The DSMB will hold regular meetings to review the trial's progress and ensure the research's quality. Please see the attachment for the full membership list. The main members include:

Chairman: [name] is an Associate Professor at West China School of Public Health, Sichuan University, Chengdu, Sichuan, People's Republic of China.. Her research focuses on adrenal disorders, particularly primary aldosteronism. She has rich clinical experience in the clinical diagnosis and treatment of adrenal diseases.

12.1 Case Report Form (CRF)

The CRF is completed by the investigator based on the original examination report, medical history collection, and physical examination results. The CRF should be completed timely and ensure that the data entered can be traced from the original record. When modifying data, you need to enter the reason and time for the modification and sign the name. Authorized personnel is required to confirm the authenticity, completeness, and timeliness of the CRF data and to sign it. Paper CRF will be made by the researchers into electronic data for analysis. Before the database is locked, the research team needs to complete the data cleaning and hold a DSMB meeting to determine the analysis population. Decisions made during the DSMB meeting should be documented. After the DSMB meeting is passed, the research team confirms that the research database in the electronic system is locked, and the data cannot be changed after the lock.

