5.3 Drug Supplies

After eligible patients randomized into treatment groups, an investigator will dispense the corresponding medication based on the group assignment of the patients.

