10.1 Analysis Populations

The following analysis populations are defined for the different types of data analysis:

• Intention-to-treat (ITT) Population

The ITT Population will include all patients randomized into the study. Treatment classification will be based on the randomized treatment;

• Modified intention-to-treat (mITT) Population

The mITT Population will include patients randomized and received at least 1 dose of any study drug. Treatment classification will be based on the randomized treatment. The mITT population will be used for the primary analysis of all efficacy endpoints;

• Per Protocol (PP) Population

The PP Population will include all patients in the mITT population and who did not experience a major protocol deviation that potentially impacted the primary efficacy endpoint. The PP population, along with the reason for exclusion, will be finalized prior to study end.

Safety Population

The Safety Population will include all patients who receive at least 1 dose of any randomized study drug. Treatment classification will be based on the actual treatment received. The Safety Population will be the primary population used for the safety analyses.

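### Per-protocol membership, which needs judgement, is left to a DSMB meeting although that board receives efficacy summaries during the trial

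*Protocol*

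**What the plan says.** **Who decides, and when.** Protocol section 12.1 has the research team clean the data and then "hold a DSMB meeting to determine the analysis population". Decisions at that meeting are to be documented. Lock comes next: "After the DSMB meeting is passed, the research team confirms that the research database in the electronic system is locked". No data may change afterwards.

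**What the board has seen.** Section 11 describes periodic DSMB reviews at which "the DSMB will receive summaries of study conduct measures as well as safety and efficacy data". It adds: "The DSMB may recommend discontinuing enrollment for a dose for safety or lack of efficacy".

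**What there is to decide.** Section 10.1 defines four sets. ITT is everyone randomized. mITT is everyone randomized who took at least one dose, and "The mITT population will be used for the primary analysis of all efficacy endpoints". Safety is everyone dosed, classified by treatment actually received. PP is the mITT set less patients who "experience a major protocol deviation that potentially impacted the primary efficacy endpoint". On its timing: "The PP population, along with the reason for exclusion, will be finalized prior to study end".

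**Masking.** Section 5.3 says that after randomization "an investigator will dispense the corresponding medication based on the group assignment of the patients". No section says that the population decision is made without knowledge of treatment or outcome.

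**The concern.** A monitoring board is given accruing efficacy data so that it can protect patients. For the same reason it should not then decide which patients count in an analysis. Someone who knows which way the results point can, even without intending it, call a borderline deviation major in one arm and minor in the other.

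Section 10.4 sizes the trial for non-inferiority. In such a trial, non-adherence and added treatment can draw the arms together and make a difference harder to see. A PP analysis is the usual companion to the mITT analysis for that reason, and it is useful only if its membership was settled without regard to outcome.

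**Working it through.** **1. Does the decision fall to people with efficacy knowledge?** Section 11 gives the board efficacy summaries, and section 12.1 gives the board's meeting the population decision. Both are stated rules about the same body, and no other section separates the two roles.

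**2. Are the summaries split by arm?** The protocol does not say so. Advising that a dose be stopped for lack of efficacy implies some comparison by treatment, so by-arm access is a reasonable inference and no more.

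**3. Which sets leave room for choice?**

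| Set | Rule in 10.1 | Judgement needed |
|---|---|---|
| ITT | randomized | no |
| mITT (primary efficacy) | randomized, at least one dose | no |
| Safety | at least one dose, by actual treatment | no |
| PP | mITT without a major deviation that may have affected the primary endpoint | yes |

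Section 12.1 speaks of the analysis population without limiting it to PP, but only PP gives a meeting anything to decide.

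**4. Do 10.1 and 12.1 agree on timing?** Study end is not defined.
- If it includes cleaning and lock, the two sections are compatible.
- If it means the last Visit 7, a PP set closed before then could not take account of Week 12 deviations, such as an ambulatory recording that fails the section 9 validity standard.

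This is an ambiguity, not a demonstrated contradiction.

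**5. The plan's own figure.** Inputs from section 10.4: SDs 12.5 and 9.5 mmHg, margin 4 mmHg, one-sided α 0.025, power 80%; a true difference of zero is assumed.
- Averaged SD = √((12.5² + 9.5²)/2) = √123.25 = 11.10 mmHg.
- n per arm = 2 × (1.960 + 0.842)² × 123.25 / 4² ≈ 121, or 242 in total.
- The noncentral t calculation gives 122 per arm (power 0.8004), or 244 in total, as stated.
- Dropout: 122/0.8 = 152.5, rounded up to 153 per arm, 306 in total, as stated.

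This point leaves the sample size untouched.

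**6. A hypothetical worst case, for the PP analysis only.** Assumptions, none from the protocol except the SDs, margin, α and 122 per arm:
- normal data and a pooled t-test of non-inferiority on the PP set;
- a true difference equal to the margin, so that a finding of non-inferiority is false;
- the finerenone patients with the worst blood pressure change are removed in full knowledge of outcome, and no spironolactone patient is removed;
- 20,000 simulated trials per row.

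| Finerenone patients removed | Mean shift in difference (mmHg) | False non-inferiority |
|---|---|---|
| 0 | 0.00 | 2.55% |
| 1 | −0.27 | 4.1% |
| 2 | −0.50 | 5.6% |
| 3 | −0.71 | 8.1% |
| 5 | −1.13 | 14.1% |

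Five removals move the estimate by 1.13/4 = 28% of the margin. This shows how few chosen exclusions would matter at the extreme. It does not predict what this board would do.

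**The case against.** **The primary analysis is not exposed.** A reader might infer that the primary result itself can be selected. It cannot, on the stated rules: mITT membership depends on randomization and one dose. The protocol also gives PP no stated part in the non-inferiority conclusion, and section 10.2 says that no formal hypothesis testing will be done. This stands, and it limits the point to a supporting analysis.

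**Summaries are not patient records.** A reader might also infer that the board knows each patient's arm and outcome. Section 11 speaks only of summaries and does not say that they are by arm. The stopping rule refers to a dose, although patients are randomized to a drug. Whether patient-level outcomes are shown at the pre-lock meeting is not stated. This stands as well: the worst case above needs knowledge that the protocol does not say the board has. Knowing the direction of the results is still enough to colour a borderline judgement.

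**Safeguards exist.** Decisions are documented, reasons for PP exclusion are recorded, and the decision comes before lock. These help a later reader to audit the choice, but they do not take away knowledge of the results.

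**The timing may be harmless.** An inadequate ambulatory recording must be repeated (section 9), and prohibited drugs still in use 2 weeks before the last visit are a withdrawal criterion (section 4.3). Some late deviations are therefore handled elsewhere, and a flat contradiction between 10.1 and 12.1 is not shown.

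**Detail may sit in the SAP.** Deviation rules and masked review are commonly left there, and their absence here is no fault. The objection does not reach section 12.1, which itself names the DSMB as the deciding body.

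**Moving the decision may not mask it.** Investigators dispense by assigned group, so site clinicians may know their patients' arms. This is a fair warning about the remedy, and the fix allows for it.

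**Conclusion.** The point holds for the PP set. Section 12.1 assigns a judgement about who is analysed to a board that section 11 supplies with efficacy data, and no section masks that judgement. The primary mITT analysis, the ITT and Safety sets and the sample size are unaffected.

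The actual size of any bias cannot be derived from the documents. The simulated rates are an extreme under stated assumptions and apply only if non-inferiority is tested on the PP set. That the board sees results by arm is inferred. The timing wording in 10.1 is an ambiguity that should be removed. This is a correction that should be made because it closes a route to bias at little cost; it is not a defect that undermines the trial's main result.

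**What to change.** **Section 12.1.** Replace the sentence on the DSMB meeting with wording to this effect: *PP membership is assigned after the last Visit 7 and before database lock, from deviation listings that carry no patient identity, treatment arm or blood pressure outcome. The reviewers have not seen DSMB efficacy summaries and did not treat the patients under review. Each exclusion and its reason are documented.* If the trial statistician prepares the DSMB reports, which the protocol does not say, someone else should take that seat.

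**Section 11.** Limit the DSMB to monitoring and state that it takes no part in assigning analysis populations.

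**Section 10.1.** Change the timing of PP finalization to *after last patient last visit and before database lock*, so that it agrees with 12.1.

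**Cost.** Protocol wording, and the preparation of masked listings for a review that replaces a meeting already planned. No visit, endpoint or sample size changes.

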12.2 Data Quality Assurance

To ensure the data reliable, the following items are made:

- Guidance materials are provided to research centers;
- Provides training and guidance to researchers and research coordinators. This training will provide relevant research protocols, case report forms (CRF);
- Regular visits to the research centers;
- Receive consultation and contact with research center staff through email, phone, we-chat, etc., to review and verify the accuracy of reported data.

In addition, data will be checked periodically against source files located at the study

center. The investigator will keep all raw data (e.g. laboratory test results, medical records, etc.)

12.3 Data accuracy

Two researchers will independently input the data to generate two sets of databases. Subsequently, data analysis software was used for consistency checks to ensure the consistency of the two sets of databases. If any inconsistencies are found, the data will be corrected by re-examining the original case report form or laboratory report. This method can effectively reduce the possible errors in the process of data entry, and ensure the accuracy and reliability of data.

13 Investigator Requirements and Quality Control

13.1 Ethical Conduct of the Study

Good Clinical Practice (GCP) is an international ethical and scientific quality standard for designing, conducting, recording, and reporting studies that involve human patients. Compliance with this standard provides public assurance that the rights, safety, and well-being of study patients are protected, consistent with the principles that have their origin in the Declaration of Helsinki, and that the clinical study data are credible. The ethics committee of The First Affiliated Hospital of Chongqing Medical University approved the protocol.

13.2 Informed Consent

The ICFs must be in compliance with local regulatory requirements, and legal requirements. The Investigator must ensure that each study patient is fully informed about the nature and objectives of the study and possible risks associated with participation and must ensure that the patient has been informed of his/her rights to privacy. The Investigator will obtain written informed consent from each patient before any protocol-specific activity is performed and should document in the source documentation that consent is obtained prior to enrollment in the study. The original signed copy of the ICF(s) must be maintained by the Investigator. A copy of the signed ICF(s) will be given to the patient.

Appendix A: schedule of procedures

¥7°	Screening and Randomization			Treatment											
Visit Week (Period window)	Visit 1 Week -2~0	Visit 2 Week 0 (+/-0)	Visit 3 Week 2 (+/-5 days)	Visit 4 Week 4 (+/-5 days)	Visit 5 Week 8 (+/-5 days)	Visit 6 Week 10 (+/-5 days)	Visit 7 Week 12 (+/-5 days)								
								n- and exclusion criteria	√	√					
								nformed consent	\checkmark						
Randomization		\checkmark													
Office blood pressure and heart rate	\checkmark	\checkmark		\checkmark	\checkmark		\checkmark								
Iome blood pressure			\checkmark			\checkmark									
Ambulatory blood pressure	\checkmark						\checkmark								
Medical history/Prior medication	\checkmark	\checkmark	√	\checkmark	\checkmark	\checkmark	\checkmark								
AE assessment and Pregnancy	\checkmark	√	\checkmark	\checkmark	\checkmark	\checkmark	\checkmark								
ECG	\checkmark			\checkmark	\checkmark		\checkmark								
Laboratory examination															
ARR	\checkmark			\checkmark	\checkmark		\checkmark								
Blood routine	\checkmark														
Urine routine	\checkmark														
Liver function	\checkmark														
Renal function	\checkmark			\checkmark	\checkmark		\checkmark								
Potassium	\checkmark			\checkmark	\checkmark		\checkmark								
UACR	\checkmark						\checkmark								
Study drug dispense	\checkmark			\checkmark	\checkmark		\checkmark								
Compliance assess	\checkmark	\checkmark	√	\checkmark	√	√	\checkmark								
Guidance adherence	\checkmark	\checkmark	√	√	√	√	\checkmark								
Provide instructions for next visit		\checkmark	\checkmark	\checkmark	\checkmark	\checkmark
